Several protocol features diminish the chance that study participants will leave the bar lab before dismissal by study staff and we have plans in place in case this occurs. As part of the informed consent process, we advise all participants of study requirements, including the requirement to stay until their BrAC falls to a safe level. We reiterate these requirements verbally and in the form of a printed handout the day before the alcohol drinking session and on the day of the session, just before the beginning of the alcohol self-administration period. Thus, participants are made aware multiple times of the requirement to remain in the facility for at least two hours after the end of the alcohol drinking period and until they reach a safe BrAC, along with other study requirements.

The pay structure of the study also discourages early departure. We pay participants \$40 per alcohol drinking session, however participants will receive only a prorated portion of the payment should they end the session early. While there is a possibility of some benefit to participants in the form of referrals for behavior change that we will provide at the conclusion of the second alcohol drinking session (participants in the heavy drinking group will also receive a brief motivational interview including personalized information about their drinking), participants in laboratory studies take part primarily for the monetary compensation, making it unlikely that they will intentionally engage in behaviors that are certain to reduce their payment.

Nonetheless, it is possible that a participant could elect to leave the research facility early. We have procedures in place should this occur. Study staff will ask individuals

who wish to end their participation early to remain in the facility until their breath alcohol reaches the safe level of 0.02% or lower. Study staff will offer these participants transportation to their home, provided for by the study regardless of their willingness to remain in the research facility until their BrAC reaches a safe level.

Administration of alcohol to individuals in treatment for addictive behaviors could potentially impede the progress of their recovery. As a result, we will not enroll individuals who have taken part in inpatient or intensive outpatient treatment for alcohol use or other addictive behaviors in the past 12 months. Further, we will not enroll individuals with a lifetime history of clinically significant withdrawal from alcohol; a lifetime history of medical intervention for withdrawal or who currently present in a manner suggestive of withdrawal, based on the Clinical Institute Withdrawal Assessment for Alcohol (CIWA-Ar). These steps regarding withdrawal will also have the benefit of excluding individuals who are severely dependent on alcohol, for whom alcohol consumption in this study may not be safe. Study activities take place in a controlled, simulated bar lab environment.

Interviews, rating scales and questionnaires: The major risk of the assessments is potential loss of confidentiality, which we address above. To minimize any discomfort associated with reporting sensitive behaviors, participants will be informed that they may refuse to respond to questions that they are not comfortable answering. Questions related to eligibility determination and monitoring of safety and treatment response are not optional. If a person declines to answer these questions, we will advise them that they will not be able to participate.

Confidentiality: Whenever possible, research participants will be referred to by study-assigned ID numbers rather than by their name or other personal information. Accordingly, results of clinical interviews, vital signs, breath alcohol and urine drug/pregnancy screening are recorded by staff members on paper forms using study IDs only. Urine testing will take place only at our research offices. Urine samples will be used for the purposes of this testing only and will be discarded after tests are completed.

However, some private identifiable information about individuals will be collected to enroll and contact participants. This information will be collected primarily via paper forms, which will be stored in locked filing cabinets in a locked room in the research facility in Yon Hall North. This includes a master list connecting participant study identification numbers to participant names.

Electronic mail is an invaluable means of communicating with prospective and enrolled study participants. All email communication with participants in this study will be via secure email accounts administered by the University of Florida. In the proposed study,

electronic mail is an option for prospective participants to self-identify as being potentially interested in the study. Prospective participants also have the option of communicating with study staff by phone. Email communication will be used primarily to schedule appointments and to respond to questions about the study. Telephone and in-person are the preferred methods for conversations regarding protected health information (PHI). Conversations via email regarding PHI will occur only after participants consent to engaging in these conversations via email after being advised of potential risks of breach of confidentiality, which will be minimal given our use of secure email accounts administered by the University of Florida.

Some self-report data will be collected via the web, however no protected health information (PHI) will be collected via web-based forms on REDCap. Participants will be identified on web-based forms in REDCap by a study-issued identification number. Even though no PHI will be collected on these forms, steps will be taken to maintain the confidentiality of this information. Data transmitted from the server will be encrypted and secured within a password-protected file that will only be accessed by study staff. These steps will provide the highest level of security for web-based data in this study.

In order to be compensated, participants' identifiable information will be entered into a secure, online system maintained by the University of Florida. Participants' names, street addresses and social security numbers will be entered into this system, however no study data will be entered and study id will not be included either thus preventing study data from being linked to the identifiers stored in this system. Use of this system enables us to compensate participants via a debit or gift card to which funds can be added as participants complete different stages of the study. Social security numbers will be collected only for the purpose of providing payment.

Electronic data sets not containing any PHI will be stored on the P.I.'s desktop computer in his office at Florida Gym, on computer in the research facility in Yon Hall North and on space in a secure server maintained by the University of Florida. Any data from this study that is shared with collaborators or other qualified individuals from institutions outside the University of Florida with whom we may collaborate on secondary data analyses will first be de-identified. Thus, no investigators outside the University of Florida will have access to any protected health information collected in this study. Individually identifiable health information will be protected in accordance with the Health Insurance Portability and Accountability Act of 1996. All research personnel will be trained on human participants' protection and HIPAA procedures.

Video recorded data will be used for data analysis conducted by authorized research team members only. No unauthorized individuals can have access to the video recordings. If there is need to use the video for educational purpose, it will not be done until the participants give us written permission. The recordings will be stored in a

locked file cabinet and linked with a code to subject's identity. Participant's name will not be revealed in the videotape. After the data analysis is completed, the video recordings will be retained for one year in case there is a need for go back to the original recording for validation. The video recordings will be destroyed after that.

In Case of Injury: If a participant is injured as a direct result of participation in this study and is clearly in need of immediate emergency treatment, 911 will be called right away. Study physician [name] will be consulted in the case of any injury. In the case of injuries that are not clearly emergencies, the next steps will be taken in accordance with [name] advice. Efforts will be made to assist participants in obtaining any necessary treatment. If injury is a direct result of study participation, healthcare will be provided at the University of Florida Health Science Center at no charge. The participant and/or his or her insurance carrier will be expected to pay the costs of any further treatment, including any treatment at Shands Hospital. No additional financial compensation for injury or lost wages is available. Participants will not waive their legal rights by participating in this study. Participants will be provided with this information as part of the informed consent process.

9. Possible Benefits

Participants may not benefit directly from study participation. They will receive referral information should they be interested in changing their drinking behavior at the conclusion of the second alcohol drinking session. Participants in the heavy drinker group will also be engaged in a motivational interview including personalized feedback regarding their drinking behavior. Should the participant decide after the first alcohol drinking session not to return for the second session or if the investigators decide in the interim to limit study participation to one session per individual, referral information will be offered by electronic mail or postal mail. For heavy drinking participants in this scenario, a motivational interview will be offered either in person or by telephone. The results of this study could benefit society at large by exploring the possibility of using videotaped topography data as an inexpensive and noninvasive objective measure to indicate AUD. The development of such measures could be widely applied for those who seek more individualized treatment based on their own drinking behavioral patterns.

10. Conflict of Interest

None.

11. Data Safety and Monitoring Plan

Designation of Serious Adverse Events:

[name], the Co-PI in charge of overseeing the data collection, has primary responsibility for monitoring the data, assuring protocol compliance, and conducting regular safety reviews after each alcohol drinking session has been completed. [name] will have primary responsibility for distinguishing serious from non-serious adverse events and has sufficient clinical research expertise to make this distinction. In addition to his own experience conducting clinical research for several years, [name] will also base determination of serious adverse events on consultation with Co-PI [name] [name], who has over 20 years of clinical and behavioral research experience. In addition, [name] will consult with Study Physician [name] regarding medical issues associated with a Serious Adverse Event.

Reporting of Serious Adverse Events

[name] will report serious adverse events in writing within 48 hours to the UF IRB 01 following their policies. The investigator will apprise fellow investigators and study personnel of all adverse events that occur during the conduct of this research project through regular weekly study meetings. An annual report will be submitted to UF IRB 01 summarizing all adverse events.

Female participants:

Women who are pregnant or nursing, or who report engaging in sexual activity with an opposite sex partner and refuse to use a reliable method of birth control (e.g., condoms +spermicide; birth control pills, diaphragm) will not be allowed to participate in this study. Urine pregnancy tests will be completed at the in-person screening appointment and at an appointment at the research office just prior to alcohol self-administration.

Supervision of Alcohol Administration Sessions:

The National Advisory Council on Alcohol Abuse and Alcoholism - Recommended Council Guidelines on Ethyl Alcohol Administration in Human Experimentation - Revised May 2005 will be followed. All alcohol drinking sessions will be supervised by [name] himself or by a graduate student or other senior research staff member who will be carefully trained in alcohol self-administration methods and this specific protocol. [name] will either be present at the alcohol drinking session himself or readily available on call to make any determination regarding serious versus non-serious adverse events. In addition, the Study Physician [name] will be available for consultation as needed. In cases of illness or injury where medical treatment is needed, the necessary treatment will be provided.

Procedures for Data Quality Assurance and Confidentiality:

Data quality will be ensured through training of research staff, the development of data collection tools, and monitoring of data quality. Study staff will monitor the quality of data after completion of each participant. Right to privacy for participation in this research will be protected through coding of data using study-assigned identification numbers and proper storage of research records. Access will be limited to the co-P.I.s and their designates involved in the study. A master list linking participants' names to their study ID numbers will be maintained, but it will be stored in a locked cabinet separate from other study materials. Identifiers will be destroyed when all study activities are completed. Protected health information will not be collected or stored electronically. Web-based data collection using REDCap will be encrypted and stored on secure servers, but will not contain any identifiers. Individually identifiable health information will be protected in accordance with the Health Insurance Portability and Accountability Act of 1996. All research personnel will be trained on human participants' protection and HIPAA procedures.

References

1. NIAAA. Alcohol facts and statistics 2017; <https://www.niaaa.nih.gov/alcohol-health/overview-alcohol-consumption/alcohol-facts-and-statistics>. Accessed Feburary 10, 2017.

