General inclusion & exclusion criteria: Participants must be 21-55 years of age, able to read English and complete study surveys, report liking beer and consuming it at least once in the past 30 days, and report having consumed at least two alcoholic drinks on at least one day during the past 30 days (i.e., current drinkers). Participants will be excluded if their urine drug test indicates recent use of illegal drugs (except cannabis) and pregnancy for women. In addition women who report engaging in sexual activity with opposite sex partners without use of reliable birth control will be excluded. Participants will also be excluded for any of the following conditions: a history of medically-assisted detoxification; present with signs of current alcohol withdrawal; currently meet the severe threshold for alcohol use disorder according to DSM-5 (i.e., 6 criteria or more); currently meet DSM-5 substance use disorder criteria at any level (i.e., 2 or more criteria) for any substance besides alcohol; are currently seeking treatment for problem substance use; have engaged in intensive outpatient or inpatient treatment for substance use in the past 12 months; meet criteria for severe depression or have any serious psychological or medical history that contraindicates alcohol consumption; currently taking any medication that contraindicates alcohol use at the levels included in this study; and have BMI under 18.5 or over 35. Given that video recording is a critical aspect of the study, participants will be required to agree to video recording in order to take part in the study. Undergraduates enrolled at the University of Florida will be excluded from participating. Graduate and non-matriculating students will be allowed to participate as long as they are not enrolled in the College of Health and Human Performance.

Subgroup division: Participants will be further divided by drinking status (social vs. heavy drinkers) and mental health status (elevated vs. non-elevated depressed mood). This creates four combinations of subgroup category (2×2). Efforts will be made to recruit equal numbers of men and women in each of the 4 categories.

Sample size: As a pilot study, we will target enrollment of up to 40 participants (~10 in each subcategory as defined in the previous section).

Procedure

Pre-screening by phone:

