Study staff will conduct a brief phone screen to determine whether the participant meet the general criteria to be included in the study. If the participant is eligible based on the phone screen, study staff will schedule an appointment for in-person screening.

Screening phase:

An in-person screening will be conducted to give information about the study and determine eligibility. The initial screening appointment will take about 2 hours. During this appointment, we will interview the participants about their drinking habits, cigarette use, mood, menstrual cycle if female, medical and mental health histories. Participants will also be engaged in a timeline followback interview to update their alcohol, cigarette smoking and electronic cigarette use. The alcohol drinking that is part of this study may not be safe for those who are also using cocaine, opiates, phencyclidine, amphetamines, methamphetamine, barbiturates, methadone or benzodiazepines. For this reason, individuals whose urine drug test indicates use of one of these drugs will be excluded. Also, participants who arrive with a positive breath alcohol reading no higher than 0.02% may be able to remain at the research office until their breath alcohol level declines to 0.00% and then continue with the appointment or reschedule the appointment one time. However, individuals who arrive at an appointment with a positive breath alcohol reading a second time will be excluded from the study and offered local referral options for treatment. Finally, women who are pregnant, nursing or sexually active with opposite sex partners without use of birth control will not be able to participate in the study.

As part of the screening procedure, participants will be asked to complete a web-based questionnaire that covers topics including drinking motives; current drinking behaviors; reasons for drinking; and physical activity level.

Information will also be gathered to categorize the participants into subgroups based on their drinking behaviors and depressive symptoms:

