- a. *Drinking behaviors:* Past 30-day drinking behaviors and DSM-5 criteria for alcohol use disorder will be used as the basis for distinguishing social and heavy drinkers. The social drinker group will be those who (1) consume at least 1 but no more than 5 standard alcoholic drinks per week and (2) engage in infrequent binge drinking (i.e., 5 or fewer times per year, but allowing for 1 past interval of a maximum of 6 months' duration of up to twice weekly binge drinking). The heavy drinker group will be those who (1) consume at least 10 alcoholic drinks per week ; (2) engage in regular binge drinking (i.e., consume 5 or more drinks on one occasion or ≥ 4 for women 1 to 5 times on average per week); and (3) meet DSM-5 criteria for mild or moderate alcohol use disorder. These criteria are based on criteria outlined by King et al.¹⁹ The timeline followback (TLFB) interview will be used to obtain self-reports of drinking behavior with a focus on past-30-day behavior, however the extent to which recent drinking behavior resembles past-12-month and lifetime drinking behavior will be queried in order to make sure participants meet criteria for

one of these two categories. Those who drink but who did not clearly fall into one of these two groups will be excluded from participation.

- b. *Depression:* Patient Health Questionnaire (PHQ-2 and PHQ-9) will be used for depression screening. The non-elevated depressed mood group will be those who scored less than 3 on PHQ-2 (i.e., negative PHQ-2). Elevated depressed mood group will be those who scored 3 or more on the PHQ-2 (i.e., positive PHQ-2) and 5 or more on the follow-up PHQ-9. Those who scored 20 or more (i.e., severe depression) will be excluded from the study and offered local referral options for treatment.

Once the participants pass the breath alcohol and urine testing, and meet all the eligibility criteria, they will be scheduled for the first of two alcohol drinking sessions. Compensation for the in-person screening appointment will be \$10 for those deemed ineligible during the first hour of the appointment and \$20 for those who complete the two hour appointment, regardless of eligibility or interest in continuing with the study.

Videotaped drinking session:

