Laboratory setting: The videotaped drinking session will take place in the simulated bar laboratory, located in Yon Hall North on the UF campus. This laboratory has been established to maximize ecological validity by simulating an actual bar. Two protocols have been approved by IRB01 to take place in this laboratory setting (IRB201500990, 201600614). It includes the drinking bar itself (seats 3 people), alcohol brand signage, television, glassware, music, and a beer tap (nonoperational). A high-definition camcorder (Sony FDR-AX53, DVD format, 100 frames/s or equivalent) will be set up in the wall cabinet after the participant is seated at the bar. The distance from the camcorder to participants is around 1.5 meters. The camcorder will be adjusted each time before videotaping to focus on the upper body of the participant to capture the detailed drinking behaviors. A digital scale (IDAODAN nutrition food scale, 5kg max, 1g/0.1oz accuracy) will be set up in front of the participant on the bar counter. The scale is equipped with wireless bluetooth technology that automatically uploads measurement to the research computer. A coaster will be placed on top of the scale. Participants will return their drink to the coaster on top of the scale after each sip. Readings from the scale will not be observable to participants.

Videotaped drinking session: An initial alcohol drinking session will take place following in-person screening. Participants will be asked not to drink any alcohol on the day of an alcohol drinking session prior to coming to the lab for the session. They will also be asked to abstain from food during the 4 hour period leading up to their session.

Transportation will be provided by the study to and from the research facility using either a university-owned vehicle or a commercial transportation service. Participants can be

picked up from any convenient location in the Gainesville area though transportation after the session must be taken directly home only. Participants within an 0.5 mile radius of the research facility may be walked to and from the facility by a study staff member rather than driven.

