Participants may be selected for a follow-up appointment for the retest after 1-2 weeks, which includes repeating the same procedure alcohol drinking session procedures as their first appointment. To make data comparable, only the same type of beer as their first drinking session will be provided to them. At the outset of this pilot study, all participants will be invited for a second session, however the study Co-PIs reserve the right to limit participation to one alcohol drinking session per individual subsequently based on limitations with preliminary study funding and/or time limitations in terms of obtaining preliminary data in support of subsequent grant applications.

Compensation for drinking session:

Participants will receive \$40 for completing each drinking session, provided they complete all study procedures and remain in the laboratory until their breath alcohol level declines to .02%. Participants leaving before this point will be given a prorated payment based on a rate of \$10 per hour. Those departing before their breath alcohol declines to a safe level during the first alcohol drinking session will be excluded from the second session.

List of instruments

Pre-Screening phase:

Demographic information: Basic demographics will be collected, including age, gender, race/ethnicity, height and weight.

Frequency and quantity of alcohol consumption: Four questions will be used to assess alcohol use: (1) number of days used alcohol in the past 30 days; (2) number of binge drinking (i.e., 5 or more drinks for men, 4 or more drinks for women) days in past 30 days; (3) highest number of alcoholic drinks consumed on any given day in the past 30 days; and (4) number of binge drinking days in the past year. Five response options will be given for each question

Frequency and quantity of cigarette smoking: Two questions will be used to assess (1) number of days smoked in the past 30 days and (2) the average number of cigarettes smoked per day on the days they smoke in the past month. Five response options will be given for each question

Preferences for different alcoholic beverages: One question will assess participants' preferences for beer, wine, and/or liquor, followed by questions asking on how many days respondents have consumed each type of alcohol in the past 30 days.

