General questions regarding other inclusion/exclusion criteria: Two questions will list the other inclusion and exclusion criteria respectively, and ask participants whether or not any of the criteria pertain to them.

In-Person Screening

Withdrawal symptoms: The 10-item Clinical Institute Withdrawal Assessment for Alcohol (Revised) (CIWA-AR)²² will be used to assess severity of current withdrawal syndromes.

Depression: Patient Health Questionnaire (PHQ-2 and PHQ-9)^{23,24} will be used for depression screening.

Medical and psychiatric history: A medical and psychiatric history will be taken from all participants, which will cover the following conditions: hypertension, diabetes, high cholesterol, cardiac abnormalities, pancreatitis, renal insufficiency, cancer, pulmonary disease, thyroid conditions, history of head injury or other neurological problems, stomach or intestinal disorders and liver disease. Participants will also be asked whether they have ever been diagnosed with a psychiatric condition or received treatment for such a condition. Participants will be asked to report all medications, including over the counter medications and those that they are currently taking, including psychotropic medications. The Structured Clinical Interview for DSM-5 (First et al., 2015) will be used to classify patients according to the presence or absence of past or present alcohol and other substance use disorders.

Self-reported alcohol consumption: The Timeline Followback Interview (TLFB) (Sobel & Sobel) will be administered at the in-person screening and updated at outset of each alcohol drinking session. Participants will be given a blank calendar including memory prompts (e.g., holidays), which covers the designated time interval (the prior 30 days at initial screening) and asked to reconstruct their drinking behavior, cigarette and electronic cigarette usage over that interval. The TLFB has good test-retest reliability and good validity for verifiable events.

Family history of problem drinking: Family history is measured with a subscale taken from the *Addiction Severity Index*.²⁶ Participants are asked to indicate whether or not four classes of relatives on both their mother's and father's side ever "had a significant problem with alcohol or drugs, one that either lead to treatment or should have led to treatment."

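### On the visible text, the eight listed drugs and contraindicated medicines are checked only before the drinking-session day, with no recheck stated on that day

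*Combined protocol and SAP*

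**What the plan says.** The hazard is stated in section 6, Screening phase: "The alcohol drinking that is part of this study may not be safe for those who are also using cocaine, opiates, phencyclidine, amphetamines". The sentence goes on to methamphetamine, barbiturates, methadone and benzodiazepines, and a positive urine test for any of these excludes. The general exclusion criteria add people "currently taking any medication that contraindicates alcohol use at the levels included in this study".

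The visible text places the checks as follows.

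- **Phone pre-screen** (List of instruments, Pre-Screening phase): two general questions ask whether any of the other inclusion or exclusion criteria apply.
- **Urine dip** (Screening phase; List of instruments, In-Person Screening): it comes before scheduling. "Once the participants pass the breath alcohol and urine testing, and meet all the eligibility criteria, they will be scheduled for the first of two" drinking sessions.
- **Medicines** (List of instruments, In-Person Screening, medical and psychiatric history): "Participants will be asked to report all medications, including over the counter medications and those that they are currently taking".

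For the session day, section 6 (Videotaped drinking session) gives an instruction about alcohol, "Participants will be asked not to drink any alcohol on the day of an alcohol drinking session prior to coming to the lab", and one about food for the preceding 4 hours. It then describes a rest, a snack, the wrist monitor and the beer. It mentions neither drugs nor medicines. For the second session, "Participants may be selected for a follow-up appointment for the retest after 1-2 weeks".

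**The concern.** Both exclusions depend on the participant's state when alcohol is taken. A dip passed at screening shows nothing about a drug used afterwards, and a medication list taken at screening does not cover a medicine started since. The protocol itself treats the combination as possibly unsafe, so one expects it to be confirmed when beer is served.

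What is at stake is participant safety: someone who has since used a listed drug, or begun a contraindicated medicine, could be served two beers with no stated step to detect it. A change of medicine is plausible in this sample. At about 10 per subgroup, 2 × 10 = 20 of the 40 participants are sought for elevated depressed mood, and psychotropic medicines are among those asked about at screening. The documents give no rate of such changes, so no event count is offered.

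**Working it through.** The plan gives no figure to reproduce. The check sets every stated timing side by side.

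**Drugs covered.** Cocaine, opiates, phencyclidine, amphetamines, methamphetamine, barbiturates, methadone, benzodiazepines = 8. The list in the Screening phase text matches the dip panel in the List of instruments.

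**Stated timing of each item**

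| Item | Before the session day | On the session day | Where the session-day timing is stated |
|---|---|---|---|
| Breath alcohol | yes | yes, at the start and during | List of instruments, In-Person Screening |
| Pregnancy test | yes | yes, before drinking | Sections 8 and 11 |
| Timeline followback (TLFB) | yes | yes, "will be administered at the in-person screening and updated at outset of each alcohol drinking session" | List of instruments, In-Person Screening |
| Menstrual data | yes | yes, at the start | List of instruments, In-Person Screening |
| Drug dip (8 drugs or classes) | yes | not stated | none |
| Medication report | yes | not stated | none |

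The most relevant comparison is with breath alcohol and pregnancy, the two clear safety checks. The TLFB and menstrual data are mainly research measures; they show only that the text contains session-start updates to which a question could be added.

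**Does the In-Person Screening heading settle it?** No. Items under that heading are also repeated at sessions. The stronger evidence is that drug and pregnancy tests share one entry there, with no session timing for either. Sections 8 and 11 then supply pre-drinking timing for pregnancy alone.

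**Does another session measure cover it?** The TLFB covers drinking, cigarettes and e-cigarettes. The SAFTEE entry describes changes in health and a symptom list, with no session timing and no drug or medication question. The breathalyzer measures alcohol only.

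**Sessions concerned.** 40 participants × 1 session = 40 if the retest is dropped, as the plan allows; 40 × 2 = 80 if everyone returns.

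**Age of the dip result.** At session 1 it is g days, where g is the gap from screening to session 1; the visible text neither gives nor caps g. At the retest it is g + 7 to g + 14 days. This assumes that the dip is not repeated, so it describes the consequence and is not separate evidence of the gap.

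**The case against.** The best reply is that silence is not absence. The pregnancy test has no session timing in its own entry either, yet it is repeated. Its timing appears in text about pregnancy risk and female participants, where one would not look for a drug dip. The Overview says each session's 3-4 hours include all testing. The content of the pre-session appointment is not described beyond the pregnancy test, and the timeline figure, consent text and printed handout are not visible. Sections 8 and 11 commit to the national guidelines on alcohol administration, whose content is also not visible. Other safety items, such as the withdrawal scale, vital signs and the suicide scale, likewise lack stated session timing. Section 11 has a safety review after each session.

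Most of this stands as a limit on what can be said about practice. A reader might infer that staff would serve beer without asking about drugs or medicines; the documents do not support that, because they do not fully describe what staff do beforehand. A reader might also infer, from four rechecked items against none for drugs and medicines, that these were singled out for omission. That is not supported either, since other safety items are equally silent and two of the four are research measures.

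None of this supplies a stated session-day check. A review after session 1 is not described as asking about drugs or medicines before session 2. The handout is a reminder of requirements and is not described as a staff check.

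The other reply is that the exposure is small: two beers of about 4.5% ABV with a 30-minute break, in people who passed a dip and have no other substance use disorder. They are supervised, stay at least 2 hours and are taken home by the study. That is correct and keeps the risk low to moderate. But these measures limit the consequences of a drug or medicine taken after screening; they do not detect it.

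**Conclusion.** The concern holds as a gap in the written procedure. Across 40 to 80 sessions, the visible text leaves two exclusions that depend on current state without a stated check on the drinking day, while breath alcohol and pregnancy have one.

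The conclusion assumes that the parts not visible do not contain the recheck. If they do, one clarifying sentence in the protocol is enough. It does not extend to a large expected harm, for which the documents give no rate, or to any effect on the aims or analysis. The change is recommended as a cheap improvement in safety.

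**What to change.** At the start of each session, with the TLFB update and before beer is poured, ask about (a) use of any of the eight drugs or classes since the last visit and (b) any new or changed medicine, including over-the-counter products. Then:

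- **Drug use reported:** run the existing dip before any beer. If positive, apply the existing exclusion. If negative, proceed or reschedule at the judgment of the investigator or study physician.
- **Contraindicated medicine reported:** serve no beer that day. Reschedule if it is a short course; exclude under the existing criterion if it is ongoing.

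Add drugs and new medicines to the pre-session instructions in section 6, and to the section 8 handout if they are not already there.

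The cost is a brief question, some wording, a dip only when use is reported, and an occasional rescheduled session or excluded participant.

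Repeating the dip for everyone at the pre-session appointment is optional and not needed for the fix. It would take at most 40 to 80 kits. Women already give urine there. With the stated aim, "Efforts will be made to recruit equal numbers of men and women in each of the 4 categories", the extra samples from men would number 40 / 2 = 20 to 80 / 2 = 40. The dip covers only the eight drugs or classes, so the medicine question would still be needed.
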